24.1.12 Magnetic Resonance Imaging (MRI)

MRI at Screening will be performed for eligibility and, in addition, the presence of MRI abnormalities supporting the diagnosis of MSA (putaminal atrophy, pontine atrophy, cerebellar and middle cerebellar peduncle atrophy, presence of putaminal hyperintense rim, putaminal signal hypointensity and/or hot cross bun sign) will also be recorded.

In addition, MRI scans will be performed for evaluation of biomarkers of disease progression and safety. The scans will be evaluated by a central reader, as pre-specified in the study-specific *Imaging Charter*.

Panel 15 contains an overview for the MRI sequences and derived parameters used for evaluation of disease progression.

MRI sequencing	Description	Regions of interest
Volumetric MRI (vMRI)	Quantification of atrophy measures in brain ROIs	 caudate nucleus putamen striatum pons brain stem
Diffusion-tensor imaging (DTI)	Quantification of diffusivity measures in brain ROIs	 cerebellum caudate nucleus putamen globus pallidus pons cerebellar white matter middle cerebellar peduncle
Arterial spin label (ASL)	Quantification of cerebral blood flow (CBF) in selected brain regions	- putamen - cerebellum

Panel 15 Derivation of MRI parameters

Additional MRI sequences will be performed for assessment of safety, including 2D T2weighted, 3D T2 FLAIR, diffusion-weighted imaging and gradient-recalled echo (GRE) sequence. The last will be used to assess the presence of cerebral microhaemorrhages.

The primary analysis for the volumetric parameters will be the percentage-wise change from baseline in each region-of-interest in the actual numbers, whereas numbers normalized by the intercranial volume (head size) will be secondary.

In some instances, an alternative workflow was performed to ensure quality of data. In case where both the original and the re-analyzed value would be present, the re-analyzed value would be the one used for further analyses.

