## 2 Introduction

## 2.1 Background

#### 2.1.1 Overview

Multiple system atrophy (MSA) is a sporadic, rapidly progressing neurodegenerative disorder characterized by autonomic failure, parkinsonism and/or cerebellar symptoms (multiple system atrophy parkinsonian type [MSA-P] and multiple system atrophy cerebellar type [MSA-C], respectively). Most patients are diagnosed with MSA between 50 to 60 years of age and the mean survival from onset of symptoms is 6 to 10 years, with few surviving more than 15 years.

The pathogenesis of MSA is linked to the misfolding of  $\alpha$ -synuclein monomers and its pathological hallmark is the presence of inclusions of misfolded  $\alpha$ -synuclein (glial cytoplasmic inclusions [GCIs]) in oligodendroglia cells. The glial cells survive, while there is a loss of neurons in several brain areas, particularly in the *putamen*, *substantia nigra*, *pons*, *inferior olive*, and *cerebellum*. Neuronal inclusions also occur in MSA, most frequently in the *putamen*, *pontine nuclei*, and *inferior olivary nucleus*. Oligodendrocytes express little  $\alpha$ -synuclein messenger ribonucleic acid (mRNA), either normally or in MSA, supporting the neuronal origin of  $\alpha$ -synuclein seeds spreading the pathology. Animal models support cellular release and uptake as the mechanism of progression and spreading of the pathology.

MSA is an orphan disease. The prevalence ranges from 2 to 5 per 100,000 in the United States (US) and European Union (EU) and from 7 to 20 per 100,000 in Japan. MSA-P constitutes approximately 70% of the cases in the US and EU, while this ratio is inverted in Japan with MSA-C constituting approximately 70% of the cases in Japan.

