4.3 Secondary Endpoints, Double-Blind Period

Disease progression

• as assessed by longitudinal changes from baseline in the UMSARS Part I, and UMSARS Part II scores up to EoTDB

Function

- Change from baseline to Week 48 in UMSARS TS
- Change from baseline to Week 48 in UMSARS Part I score
- Change from baseline to Week 48 in mUMSARS score
- Change from baseline to Week 48 in UMSARS Part II score
- Change from baseline to Week 48 in Schwab and England Activities of Daily Living scale (SE-ADL)

Global impression

- Change from baseline to Week 48 in Clinical Global Impression Severity (CGI-S) score
- Change from baseline to Week 48 in Patient Global Impression Severity (PGI-S) score
- Change from baseline to Week 48 in Observer-reported Global Impression Severity of Illness (OGI-S)

Autonomic symptoms

• Change from baseline to Week 48 in Composite Autonomic Symptom Score Select Change (COMPASS Select Change) score

Global disability

• Change from baseline to Week 48 in UMSARS Part IV score

Disease milestones

- Change from baseline to Week 48 in speech, swallowing, falls, and walking, as assessed by the UMSARS Part I sub-items
- Change from baseline to Week 48 in frequency, cause and consequence of falls, as assessed by the fall diary in dedicated periods

Health-related quality of life

• Change from baseline to Week 48 in EQ-5D-5L score (individual items and VAS score)

MRI biomarkers

• Percentage change from baseline to Week 48 in brain volume in brain regions-of-interest (ROIs); primary ROIs: pons and cerebellum; secondary ROIs: caudate nucleus, putamen, brain stem and total grey matter, as measured by volumetric MRI (vMRI)

Biofluid biomarkers

• Blood: Change from baseline up to Week 48 in neurofilament light chain (NfL) concentrations

Pharmacokinetics

- Lu AF82422 plasma concentration during treatment and safety follow-up
- Lu AF82422 cerebrospinal fluid (CSF) concentrations and the CSF/plasma concentration ratios

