- A constrained longitudinal data analysis with natural cubic splines that treats time as continuous, which allows separate splines for each treatment (Donohue et al, 2023)⁶. The natural cubic spline model assumes:

$$Y_{i,j} = \beta_0 + \sum_{k=1:m} (\beta_k \cdot b_k(t_j)) + Active_i \cdot \sum_{k=1:m} (\gamma_k \cdot b_k(t_j)) + \varepsilon_{ij},$$

Study 18331A - Statistical Analysis Plan

where $b_k(t)$ are the known spline basis functions for a given set of knots and extreme values of t, with Interior knots spaced according to quantiles of t. The resulting curve for the placebo group is defined by the natural cubic spline $f(t) = \beta_0 + \sum_{k=1:m} (\beta_k \cdot b_k(t_j))$; while the natural cubic spline $g(t) = \sum_{k=1:m} (\gamma_k \cdot b_k(t_j))$ represents the treatment group difference over time and is constrained to be zero at time zero. Estimation of the unknown parameters (β s and γ s) is accomplished with maximum likelihood estimation. It is to be noted, that a special case of the spline parameterization with visit times set to the planned times and knot locations chosen to match the planned visit times is equivalent with a categorical-time mean structure as found in the MMRM.

In this case, a natural spline with one interior knot at the median observation time has been selected as proposed by Donohue et al in their paper. In addition, as covariance matrix an unstructured approach will be applied. The model will in addition be adjusted for MSA sub-type and the two categorical covariates used for stratification, i.e., Region and CCI. The primary evaluation for the spline model will be performed at Week 48 and additional time points will be exploratory.

In fitting the model, the basis for the natural cubic splines is generated using the SAS® code given in the Appendix II.

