14.4.2 Analysis Methodology for the Secondary Endpoint

- For the UMSARS Part I, UMSARS Part II and the aUMSARS, a similar Bayesian progression model and estimand strategy to the primary analysis will be applied.
- For remaining continuous secondary endpoints (e.g., clinical scales/assessments and MRI parameters), the change from baseline to EoTDB will be analysed using a restricted maximum likelihood (REML)-based mixed model for repeated measures (MMRM). The model will include the following: region, CCI and treatment (Lu AF82422 and placebo) as fixed factors, baseline as continuous covariate, treatment-by-week interaction and baseline-by-week interaction. An unstructured covariance structure will be used to model the within-patient errors. The Kenward-Roger approximation will be used to estimate denominator degrees of freedom. The analysis will be performed using all available observations (observed cases [OC] data) in the DBP. The estimated treatment differences between Lu AF82422 and placebo obtained at Week 48 will be estimated based on the least squares means for the treatment-by-week interaction in the MMRM model. Estimated treatment differences at Week 60 and 72 will be exploratory. In case of issues converging, a Toeplitz structure will be fitted instead.
- Categorical secondary endpoints will be evaluated using shift-tables evaluated at Week 48.
- Adjusted number of falls per individual per fall diary period in the DBP, according to the patient fall diary, will be analysed applying a MMRM as described above, if appropriate. Cause and consequence of falls will be evaluated descriptively.
- Time-to-wheelchair endpoint as assessed in the physical examination (first time point as 'full time user') following up to 72 weeks of treatment will be presented by a Kaplan-Meier plot and analysed applying a Cox proportional-hazards model. The model will be adjusted for stratification factors.
- Lu AF82422 plasma concentrations, CSF concentrations, and the CSF/plasma concentration ratios during treatment for all patients will be presented descriptively. A

population pharmacokinetics analysis (popPK) will also be performed and included in a separate reported.

- Absolute values and changes from baseline to EoTDB in blood and CSF biomarkers will be analysed descriptively (i.e., NfL, t-tau, truncated alpha synuclein). A MMRM will be applied for the changes from baseline to EoTDB. If required, a log transformation will be applied for normalization.

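### The vMRI model leaves out MSA sub-type, and the head-size-normalised percentage change is no independent check if volumes are divided by one head size per patient

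*SAP*

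**What the plan says.** The vMRI endpoint in SAP 4.3 is "Percentage change from baseline to Week 48 in brain volume in brain regions-of-interest (ROIs); primary ROIs: pons and cerebellum". SAP 24.1.12 ranks two versions of it. Of the first it says: "The primary analysis for the volumetric parameters will be the percentage-wise change from baseline in each region-of-interest in the actual numbers". The head-size version is ranked below that one: "whereas numbers normalized by the intercranial volume (head size) will be secondary". The section does not say whether normalisation is a ratio or a regression residual, whether intracranial volume (ICV) is measured once or at every scan, or whether the normalised numbers are also analysed as percentage change.

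The model is in SAP 14.4.2, which covers the MRI data by name: "For remaining continuous secondary endpoints (e.g., clinical scales/assessments and MRI parameters". Of its terms it says: "The model will include the following: region, CCI and treatment (Lu AF82422 and placebo) as fixed factors, baseline as continuous covariate". Interactions of week with treatment and with baseline are also included. The blacked-out term is the second stratification factor. The mixed model in Protocol 17.9.6 likewise has a baseline term and no sub-type term.

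MSA sub-type is recorded at screening (Protocol Panel 2). In the SAP it enters an efficacy model only for UMSARS: as a subgroup in 14.3.6, and in the spline sensitivity model of 14.3.5, where "The model will in addition be adjusted for MSA sub-type" on top of the two stratification covariates. Protocol 17.9.6 lists baseline MRI signal and MSA sub-type among covariates to investigate, without naming an endpoint; the corresponding list in the synopsis does not include sub-type. SAP 14.3.7, the covariate section, concerns the primary endpoint only and includes neither.

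**The concern.** There are two separate matters.

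**Sub-type.** The primary regions are the pons and the cerebellum, and sub-type divides patients into predominantly parkinsonian and predominantly cerebellar disease. It is a plausible predictor of volume loss in exactly these regions. Randomisation is not stratified by it, and with 40 v 20 patients the arms can differ noticeably. Leaving a prognostic baseline factor out of the model costs precision in a small trial.

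**Normalised analysis.** Head size does not change within an adult patient. Dividing both the baseline and the follow-up volume by the same head size leaves the percentage change as it was. If the normalised result were then shown beside the primary one as corroboration, agreement between them would be nearly built in. Head size does matter in the baseline covariate: a small raw pons volume can mean a small head or an atrophied pons, and the primary model uses the raw volume.

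**Working it through.** The documents give no power or precision figure for vMRI; the 75% power in SAP 21 concerns UMSARS progression. There is therefore no plan figure to reproduce.

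**Step 1: cancellation.** With volumes V0 and V1 and one ICV value I per patient, ratio normalisation gives

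100 × [(V1/I)/(V0/I) − 1] = 100 × (V1/V0 − 1).

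Example (illustrative volumes): 12.0 falling to 11.4 with I = 1450 gives −5.00% raw and −5.00% normalised.

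**Step 2: what still differs.** The SAP model has "baseline as continuous covariate, treatment-by-week interaction and baseline-by-week interaction". On the natural reading the primary analysis carries V0 and the normalised analysis carries V0/I. In simulation (2000 trials per scenario, Week 48 linear model, 48 patients split 32 v 16 after 20% drop-out) the outcomes were identical. The two treatment estimates nevertheless differed between trials with an SD of 0.34 points (32% of the SE) when baseline and sub-type were prognostic, and 0.14 points (14%) when neither was.

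**Step 3: if the conditions fail.** With ICV re-measured, a 1% ICV error at follow-up turns −5.00% into 100 × (0.95/1.01 − 1) = −5.94% or 100 × (0.95/0.99 − 1) = −4.04%. Error of 0.5% or 1% per scan adds about 100 × 0.95 × √2 × 0.005 = 0.67 or 1.34 points of SD, and the correlation with the raw change is 0.983 or 0.935. With residual normalisation the correlation is about 0.98. The outcome is then not identical, but it is close to the primary one.

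**Step 4: sub-type mix and region.** Protocol 2.1.1 states that "MSA-P constitutes approximately 70% of the cases in the US and EU" and that the ratio is inverted in Japan. Japan is capped at 25%.
- MSA-C share at the cap: 0.75 × 0.30 + 0.25 × 0.70 = 0.40; with no Japanese patients, 0.30.
- Sub-type variance at the cap: 0.40 × 0.60 = 0.24; within either region: 0.30 × 0.70 = 0.21.
- Share explained by region: (0.24 − 0.21)/0.24 = 12.5%, and less below the cap.

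**Step 5: precision gain after region adjustment.** Let d be the sub-type difference in percentage volume change, in units of the SD within sub-type. The documents give no value; 0.5 to 1.0 is assumed. Then R² = 0.21d²/(1 + 0.21d²), and the SE falls by 1 − √(1 − R²).
- d = 0.5: R² = 0.0525/1.0525 = 0.050; the SE falls by 2.5%.
- d = 1.0: R² = 0.21/1.21 = 0.174; the SE falls by 9.1%.

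Because 0.21 holds within each region, this range does not depend on the Japan share.

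**Step 6: simulated SE of the treatment effect.** Assumptions: residual SD 3 points, ICV coefficient of variation 0.10, MSA-C share 35% and unrelated to region.

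| Sub-type difference | V0 | V0 + sub-type | V0/ICV + sub-type |
|---|---|---|---|
| 3 points | 1.071 | 0.972 | 0.957 |
| 1.5 points | 0.994 | 0.969 | 0.955 |
| 0, baseline not prognostic either | 0.942 | 0.952 | 0.952 |

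Variance ratios for adding sub-type alone are 1.22, 1.05 and 0.98. In the last row the SE rises by 0.952/0.942 − 1 = 1.1%.

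**Step 7: chance imbalance.** The SD of the between-arm difference in MSA-C share is √[0.24 × (1/40 + 1/20)] = 13.4 percentage points, and a gap of 15 points or more has probability about 0.26. At a 30% share the figures are 12.5 points and 0.23.

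**The case against.** The strongest reply is that the plan already contains most of what is asked for. Run on normalised numbers, the SAP's own model would carry normalised baseline volume and its week interaction. A reader might infer that the normalised analysis merely repeats the primary one and that relative baseline volume is missing from the plan. The documents support neither inference. Identity of the outcomes needs ratio normalisation, a single ICV and a percentage-change outcome, and SAP 24.1.12 states none of these; the Imaging Charter may settle some of them. Even when outcomes are identical, Step 2 shows that the estimates differ. Relative baseline volume is absent only from the primary, raw-volume model. Normalised volumes also have a use in the scatterplots of absolute values planned in SAP 14.5, where head size does not cancel. Nor does the SAP call the normalised result an independent check; it calls it secondary.

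On sub-type, adjusting for stratification factors and baseline is a conventional choice at N = 60, and the spline model concerns a different endpoint. Protocol 17.9.6 does not commit the vMRI model to sub-type. The prognostic strength is assumed, and at zero the adjustment loses slightly. A reader might also count chance imbalance as a bias on top of the precision loss. It is not one: the imbalance variance is the same component that R² measures, the unadjusted SE covers it, and over randomisations there is no bias.

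All of this stands as a limit on the point. It does not remove the case for adding an already recorded factor that region represents poorly and that the sponsor adjusts for elsewhere. Nor does it make the normalised percentage change independent evidence.

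**Conclusion.** The point holds as a low-severity improvement. MSA sub-type is absent from the vMRI model in both documents, and region stands in for at most about 12.5% of its variance. Adding it would cut the SE of the Week 48 contrast by roughly 2.5 to 9% if sub-types differ by 0.5 to 1.0 SD, and would raise it by about 1% if they do not differ. The size of the difference is an assumption; the MSA-C share of 30 to 40% follows from the protocol's regional mix and the 25% cap on Japan. These figures come from a Week 48 model. A sub-type term without a week interaction fits one average difference across visits, so the gain may be smaller if the difference widens with time.

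The normalised percentage change is the same outcome as the primary one if ICV is one value per patient and normalisation is by ratio. Under the other readings checked it is a close relative (correlation 0.935 to 0.983). In no case checked is it independent support.

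vMRI is a secondary endpoint outside the fixed sequence in SAP 15.2, which covers only UMSARS TS and mUMSARS. No confirmatory conclusion depends on this.

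**What to change.** In SAP 14.4.2, for vMRI:
- add MSA sub-type (MSA-P/MSA-C) as a fixed factor;
- use baseline volume divided by baseline ICV, with its week interaction, as the continuous covariate.

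In SAP 24.1.12:
- keep percentage change in actual volume as the outcome;
- state how volumes are normalised and whether ICV is measured once or at each scan;
- state that the percentage change in normalised volume is not presented as independent support for the primary vMRI result.

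The cost is SAP wording before unblinding and one model degree of freedom, with an SE about 1% larger if sub-type turns out not to be prognostic. Sub-type is already recorded at screening, and ICV is needed for the normalisation already planned.

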24.2 Assigning Data to Visits

Invalid assessments will be assigned AVISTN = 888. If the date of last dose is missing, assessments will be considered valid. If multiple assessments are taken the same day, only the last assessment will be valid. Invalid assessments will not be considered in descriptive statistics or statistical analyses but will be included in listings of safety variables.

Assessments at *unscheduled and withdrawal visits* will be assigned to a target day (AWTARGET) based on days after baseline visit, and to an analysis week (AVISTN = AWTARGET/7). Assessments falling outside a defined visit window will be evaluated and will be deemed invalid (AVISTN = 888) for that specific windowing approach in case no obvious week can be identified.

24.2.1 UMSARS and additional efficacy COAs

For UMSARS, both a narrow and a broad approach will be applied for assigning observations to a visit: 1) observations will be mapped to the nearest official clinical visit in 4-weeks intervals, independent whether UMSARS originally was scheduled for this visit, and 2)

observations will be mapped to the nearest official UMSARS visit in 12-weeks intervals according to protocol.

Nominal Vis Number (DB-Period)	Nominal Vis Week	Nominal Vis Day	Time Window narrow ¹	Time Window broad ¹
V1 (Screening Visit)	-6	-42	NA	NA
V3 (Baseline Visit)	0	0	-7 to 7	-7 to 7
V5 (WD Visit)	4	28	15 to 42	NA
V7 (WD Visit)	8	56	43 to 69	NA
V9 (planned UMSARS/WD Visit)	12	84	70 to 98	15 to 126
V10 (WD Visit)	16	112	99 to 126	NA
V11 (WD Visit)	20	140	127 to 154	NA
V12 (planned UMSARS/WD Visit)	24	168	155 to 182	127 to 210
V13 (WD Visit)	28	196	183 to 210	NA
V14 (WD Visit)	32	224	211 to 238	NA
V15 (planned UMSARS/WD Visit)	36	252	239 to 266	211 to 294
V16 (WD Visit)	40	280	267 to 294	NA
V17 (WD Visit)	44	308	295 to 322	NA
V18 (planned UMSARS/EoTDBP/WD Visit)	48	336	323 to 350	295 to 378
V19 (EoTDBP/WD Visit)	52	364	351 to 378	NA
V20 (EoTDBP/WD Visit)	56	392	379 to 406	NA
V21 (planned UMSARS/EoTDBP/WD Visit)	60	420	407 to 434	379 to 462
V22 (EoTDBP/WD Visit)	64	448	435 to 462	NA
V23 (EoTDBP/WD Visit)	68	476	463 to 490	NA
V24 (planned UMSARS/EoTDBP Visit)	72	504	491 to 518	463 to 518
Nominal Visit Number (OLE-Period)				
V1E (baseline OLEP Visit) ²	0E	0	-7 to 7	-7 to 7
V2E (WD Visit)	4E	28	15 to 42	NA
V3E (WD Visit)	8E	56	43 to 69	NA
V4E (planned UMSARS/WD Visit)	12E	84	70 to 98	15 to 126
V5E (WD Visit)	16E	112	99 to 126	NA
V6E (WD Visit)	20E	140	127 to 154	NA
V7E (planned UMSARS/WD Visit)	24E	168	155 to 182	127 to 210
V8E (WD Visit)	28E	196	183 to 210	NA
V9E (WD Visit)	32E	224	211 to 238	NA
V10E (planned UMSARS/WD Visit)	36E	252	239 to 266	211 to 294
V11E (WD Visit)	40E	280	267 to 294	NA
V12E (WD Visit)	44E	308	295 to 322	NA
V13E (planned EoTOLE Visit)	48E	336	323 to 350	295 to 350

Panel 16 Visit Windows for UMSARS

All post-baseline visits (except EoT visits) can be converted into a Withdrawal (WD) Visit. ¹ For DBP and OLEP, respectively, the applied narrow window will be continuous (i.e., ± 14 days) to avoid invalid assessments (protocol text ± 3 days). The broad window is set up as continuous as well to match. ² EoTDBP Visit will work as Baseline Visit for the OLEP if done within the acceptable window.

Records to be used in descriptive statistics or statistical analyses will be flagged with ANL01FL=Y and ANL02FL=Y. ANL01FL = Y and ANL02FL=Y will be assigned to all valid assessments (NOMWEEK not equal to 888) unless an assessment at the Withdrawal Visit or an Unscheduled Visit is assigned to the same analysis week as a scheduled visit (having the same NOMWEEK). In this case, ANL01FL = Y will be assigned to one valid visit prioritized in the following order: Scheduled Visit, Unscheduled Visit, and Withdrawal Visit.

CGI-S, PGI-S, and OGI-S will follow the same windowing principles since these were administered at the exact same visits as the UMSARS. The remaining COAs, i.e., SE-ADL, COMPASS Select Change and EQ-5L-5D were only administered at Week 24, 48 and 72 (Visit 12, 18, and 24) post-baseline in the DBP, and hence the broad windowing will only contain these visits using the above intervals, meaning that some observations might be deemed invalid for this mapping. However, they will be mapped into the above narrow windows as well using the continuous windowing approach. The same principles will be applied for the OLEP.

Remission in the CGI-S, PGI-S or OGI-S score (defined as a score of 1 or 2) at each analysis week following a baseline will be included as new parameters (PARAM=*Remission*).

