14.3 Analysis Methodology for the Primary Endpoint

14.3.1 Primary Analysis of the Primary Endpoint

The primary efficacy analysis following up to 72 weeks of treatment will be based on a Bayesian repeated measures model, also referred to as a Bayesian functional-impairment

progression model (BFPM), of the changes from baseline in the UMSARS TS. The BFPM incorporates the following aspects:

- Repeated measures for the change from baseline in the UMSARS TS score over the recurring 72-week's visit schedule
- Piece-wise linear rate of progression per 12-week time interval. However, does not require equally spaced intervals between observations. Time modelled continuously
- Patient-level random effect in rate of progression
- Proportional treatment effect, θ, for slowing of disease progression rate when treated relative to placebo. In particular, if θ<1, the active treatment slows the rate of progression relative to placebo. If θ>1, the active treatment increases the rate of progression relative to placebo. If θ=1, the rate of progression of UMSARS TS is the same for both active treatment and placebo
- Fixed multiplicative covariate effects in the increase or decrease in the overall rate of
 progression of UMSARS TS for categorized CCI

and region (US and Japan) common across all visits

- Prior distributions for model parameters selected in a conservative and non-informative manner using relatively large outcome spaces
- The primary analysis considers only actual observations and does not impute missing data

Let change from baseline in the UMSARS TS at visit *j* for subject *i* be labelled $Y_{i,j}$, $i = 1, ..., N, j = 1, ..., J_i$ where there are J_i total post-baseline visits for subject *i*. Change from baseline will be modelled as piece-wise linear with time intervals, k = 1, ..., K, defined every 12 weeks. Let $X_{i,j,k}$ be the exposure (time since baseline in weeks) for subject *i* at visit *j* during the time interval *k*. The MSA progression model is:

$$Y_{i,j} \sim N(\mu_{i,j}, \sigma_{t(i)}^2); i = 1, ..., N; j = 1, ..., J_i$$

$$\mu_{i,j} = 0 + \sum_{k=1:K} \left(\beta_k + \beta_{k,i} \right) * (X_{i,j,k}/12) * \theta_{t(i)} * \exp\left(\delta_{g(i)} + \eta_{r(i)} \right)$$

where each parameter is defined below and the prior distribution for the parameter is given:

 β_k : Mean expected change from baseline over each 12-week interval

$$\beta_k \sim Norm(0, 10^2)$$
; $k = 1, \dots, K$

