14.3.5 Sensitivity Analyses of the Primary Endpoint

Handling of Missing Data

The following sensitivity analyses will be performed in case of drop-out/withdrawal/death, where the below rules will be applied for the visit following the event for subjects not having

complete data from the Withdrawal Visit, assuming that intermediate missingness will be 'missing at random':

- For withdrawal due to death, impute individual missing UMSARS items as worst possible score in case of death.
- For withdrawal due to other reasons, impute individual missing UMSARS items as worst observed within-subject value for the specific item at any post-IMP time point.
- For withdrawal due to other reasons, impute individual missing UMSARS items as the worst value observed within the combined treatment and control arms at any post-IMP time point.

Two analyses will be performed in both cases using the above strategy to handle withdrawal due death. Following each of the above strategies for handling withdrawals due to other reasons will then be applied.

To explore further the impact of death, a non-parametric joint-rank analysis will be performed to account for informatively missing data by ranking patients based jointly on their Week 48 UMSARS score (UMSARS TS and mUMSARS) and 48-week survival, i.e., time-to-death. Such analysis corresponds to a composite strategy. In case of missing Week 48 data for survivors, Multiple Imputation (MI) will be performed in which the remaining missing data will be imputed corresponding to a missing-at-random assumption.

Missing data for UMSARS Week 12 up to Week 48 will be addressed by using Multiple Imputation. Missing data will be imputed using a sequential regression-based multiple imputation method, based on the imputation models established from the corresponding randomized treatment group. Example SAS code for this imputation can be found in Appendix II.

200 imputed datasets will be created, which will each be analysed and combined as follow.

Define score, u_{ij} , which is chosen to reflect whether patient i has had the more favourable UMSARS score than patient j. In the case where both patient i and j died prior to the Week 48 assessment:

- $u_{ij} = 1$ in the case where patient i died after patient j
- $u_{ij} = -1$ in the case where patient i died before patient j
- $u_{ij} = 0$ in the case where it cannot be determined who died first

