15.1 Calibrating primary analysis

The final analysis will use all available data on all enrolled participants at baseline through 48-72 weeks. A success threshold is defined for the final analysis to maintain an overall alpha of 5% evaluated one-sided. The effect of Lu AF82422 will be evaluated using a Bayesian posterior probability of superiority relative to placebo with a threshold of 97.5% identified through simulations.

Lu AF82422, CCI dose: $Pr(\theta_2 < 1) > .975;$

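### The one-record-per-week flag in SAP 24.2.1 ranks the Withdrawal Visit last, so a drop-out's final UMSARS can be left out of the analyses, and the worst-value imputation in 14.3.5 does not cover the gap

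*SAP*

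**What the plan says.** SAP 24.2.1 states what the flags govern: "Records to be used in descriptive statistics or statistical analyses will be flagged with ANL01FL=Y and ANL02FL=Y". Every valid assessment is flagged unless a withdrawal or unscheduled assessment lands in the analysis week of a scheduled visit. In that case "ANL01FL = Y will be assigned to one valid visit prioritized in the following order: Scheduled Visit, Unscheduled Visit, and Withdrawal Visit". This order is given for ANL01FL. None is given for ANL02FL, and the section does not say which flag belongs to which windowing or which windowing feeds which model.

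Two windowings are defined in the same section and in Panel 16. In the narrow one, "observations will be mapped to the nearest official clinical visit in 4-weeks intervals". In the broad one, "observations will be mapped to the nearest official UMSARS visit in 12-weeks intervals".

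On the primary model, SAP 14.3.1 says of the 12-week rate intervals: "However, does not require equally spaced intervals between observations. Time modelled continuously". That analysis takes observed values only and imputes nothing. SAP 15.1 adds: "The final analysis will use all available data on all enrolled participants at baseline through 48-72 weeks".

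SAP 14.3.5 sets out two sensitivity analyses for withdrawal and death, both built on worst values. Their rules are confined to subjects who do not have "complete data from the Withdrawal Visit, assuming that intermediate missingness will be" missing at random. A separate joint-rank analysis uses multiple imputation for survivors with no Week 48 score and carries no such condition.

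**The concern.** The last score before a patient leaves is the observation closest to whatever led to the withdrawal. An observed-case analysis that relies on data being missing at random needs that score among the data it conditions on. If the flag removes it, two things follow. The primary model loses a valid, dated observation that it could have used as it stands. The worst-value analyses, whose purpose is to test the handling of drop-outs, treat the patient as having Withdrawal Visit data and leave the gap unfilled. For that patient the end of follow-up is then neither observed nor imputed, while the sensitivity analyses appear to cover all withdrawals. With 60 patients randomized 2:1, a few such records are a noticeable share of the information on drop-outs.

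**Working it through.** **Inputs**
- 60 patients and a 20% drop-out allowance (SAP section 21): 60 × 0.20 = 12 drop-outs.
- Scheduled post-baseline UMSARS at Days 84, 168, 252, 336, 420 and 504 (Panel 16).
- Narrow windows end 14 days after each of these. Broad windows end 42 days after (14 days at Week 72, which ends at Day 518).
- Assumptions: every drop-out attends a Withdrawal Visit with a complete UMSARS, and the ANL01FL order applies in whichever windowing is used.

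The plan gives no figure for this loss, so there is none to reproduce. Its stated power of about 75% does not bear on the point. It also cannot be recalculated here, because the mean progression and SD behind it are not in the available text.

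**Two examples**
- UMSARS at Day 168, Withdrawal Visit at Day 180. Both lie in the narrow Week 24 window (155 to 182) and in the broad one (127 to 210). The Day 180 score is deselected whichever windowing ANL01FL refers to.
- UMSARS at Day 168, Withdrawal Visit at Day 196. Under broad windows both are Week 24, so the Day 196 score is deselected. Under narrow windows Day 196 is Week 28 (183 to 210), meets no competing UMSARS, and is kept.

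**Scenario A: withdrawal equally likely on any day from Day 15**

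Share lost = (scheduled UMSARS before the horizon × days from visit to window end) / (horizon − 15). Expected loss = 12 × share.

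| Horizon | Narrow | Broad |
|---|---|---|
| Week 48 (Day 336) | 3 × 14 / 321 = 13.1%, 1.6 of 12 | 3 × 42 / 321 = 39.3%, 4.7 of 12 |
| Week 60 (Day 420) | 4 × 14 / 405 = 13.8%, 1.7 of 12 | 4 × 42 / 405 = 41.5%, 5.0 of 12 |
| Week 72 (Day 504) | 5 × 14 / 489 = 14.3%, 1.7 of 12 | 5 × 42 / 489 = 42.9%, 5.2 of 12 |

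Moving the scheduled visits by −3 or +3 days widens the ranges to 10–18% (1.2 to 2.1 of 12) for narrow and 36–46% (4.4 to 5.6 of 12) for broad.

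**Scenario B: withdrawal only at the 4-weekly visits**
- Broad: collisions at Weeks 16, 28 and 40 give 3/12 visits up to Week 48, so 12 × 3/12 = 3.0. Adding Weeks 52 and 64 gives 5/18 visits up to Week 72, so 12 × 5/18 = 3.3.
- Narrow: the next visit is 28 days on, beyond the 14-day reach, so the loss is 0.

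**Imputation**

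Take a patient whose Withdrawal Visit UMSARS is complete but unflagged. The primary analysis imputes nothing. The two worst-value analyses exclude the patient, because Withdrawal Visit data exist, and nothing in 14.3.5 covers a complete but deselected record. The joint-rank multiple imputation fills a missing Week 48 score for any survivor, so it does not skip the patient, although it would not use the deselected score either.

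**The case against.** The strongest reply is that the SAP never says the larger loss will happen. The priority order is attached to ANL01FL only. The narrow windowing maps observations whether or not UMSARS was due at that visit, and so is well suited to keeping off-schedule withdrawal scores. If ANL01FL is the narrow flag and the models use it, the loss is at most about two patients, and none if withdrawals fall on the 4-weekly visits. Panel 16 allows post-baseline visits to be converted into Withdrawal Visits, which makes that pattern plausible. All of this stands, and it is why the result is a range starting at zero.

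The 12 attending drop-outs are also an upper limit. SAP 3.3 counts deaths among withdrawals, and Protocol 9.6 asks for the visit only where feasible. SAP 15.1 may describe the span of the data rather than record selection, and the code appendices that might show the selection are redacted. These points soften the conflict with 15.1 but do not remove it, since the wording of 24.2.1 covers statistical analyses generally and exempts none.

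A reader might go further and infer that the final score is always discarded, that it enters no analysis at all, or that progression in drop-outs is shown to be understated. The documents do not support these. The Day 196 example survives under narrow windows. A deselected score follows a retained one by at most about six weeks, and the patient's other data stay in the model. No mean or SD is available from which to compute a bias, overall or between arms.

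**Conclusion.** The point holds as a defect in record selection. Applied literally, SAP 24.2.1 can exclude a valid, later UMSARS from a primary model that could use it, and the two worst-value analyses then leave the gap open. This sits badly with SAP 15.1 and with what the plan intends elsewhere. SAP 14.3.3 justifies the model by its full use of patients with incomplete follow-up. SAP 14.6 uses Withdrawal Visit data in the exploratory MMRM. Protocol 9.6 says that data up to and including the Withdrawal Visit are used when a patient withdraws consent but attends.

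The size is about 0 to 2 of 12 final assessments under narrow windows and about 3 to 5.6 under broad windows. Both ranges assume full attendance with a UMSARS, and the broad one also assumes that ANL02FL follows the ANL01FL order. Which range applies to which model cannot be told from the SAP. The direction and size of any effect on the treatment estimate cannot be computed from the documents.

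**What to change.** - **SAP 24.2.1, continuous-time models.** State that the Bayesian progression model and the spline model use every valid UMSARS at its actual assessment day, Withdrawal Visits included, without the one-record-per-week flag. For the spline model, also say how the unstructured covariance is indexed, so that two records from one patient do not share an index.
- **SAP 24.2.1, visit-based MMRM.** Name the windowing used, link each flag to its windowing, and give the tie-break for ANL02FL. The tie-break should also cover two scheduled visits in one window: under broad windows an end-of-treatment visit at Week 52 or 64 shares a window with Week 48 or 60. Do not move an observed withdrawal score forward to the next UMSARS visit. A Day 196 score would be placed at Day 252, 8 weeks early, and one taken just after Day 168 almost 12 weeks early, which in a progressive disease would itself understate progression.
- **SAP 14.3.5.** Where a Withdrawal Visit record is deselected for an analysis, treat the patient as lacking Withdrawal Visit data for that analysis, so that the worst-value rules apply.

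The cost is SAP wording and a change to a record-selection flag before unblinding. No new data are needed.
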